#### 8.2 Adverse Events

An AE is defined as any untoward medical occurrence in a clinical investigation participant administered a pharmaceutical product, which does not necessarily have a causal relationship with this treatment. An AE can therefore be any unfavorable and/or unintended sign (including an abnormal laboratory finding), symptom, or disease temporally associated with the use of an investigational medicinal product, whether or not related to the investigational medicinal product. All AEs, including observed or volunteered problems, complaints, or symptoms, are to be recorded on the appropriate eCRF.

AEs, which include clinical laboratory test variables, will be monitored and documented from the time of signing of informed consent at Screening (Visit 1) until the EOS Visit (35 days after the EOT Visit). Participants should be instructed to report any AE that they experience to the Investigator, whether or not they think the event is due to study treatment. Beginning at the time of signing of informed consent, Investigators should make an assessment for AEs at each visit and record the event on the appropriate AE eCRF.

Wherever possible, a specific disease or syndrome rather than individual associated signs and symptoms should be identified by the Investigator and recorded on the eCRF. However, if an observed or reported sign or symptom is not considered a component of a specific disease or syndrome by the Investigator, it should be recorded as a separate AE on the AE eCRF. Additionally, the condition that led to a medical or surgical procedure (eg, surgery, endoscopy, tooth extraction, or transfusion) should be recorded as an AE, not the procedure itself.

Any medical condition already present at Screening (Visit 1) should be recorded as medical history and not be reported as an AE unless the medical condition or signs or symptoms present at Baseline changes in severity, frequency, or seriousness at any time during the study. In this case, it should be reported as an AE.

Clinically significant abnormal laboratory or other examination (eg, ECG) findings that are detected during the study or are present at Screening (Visit 1) and significantly worsen during the

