## 10.1.4 Medical Information Coding

For medical information, the following thesauri will be used:

- Medical Dictionary for Regulatory Activities (latest) for medical history and AEs; and
- WHO Drug Dictionary for prior and concomitant medications.

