- 11. It should be ensured that a repeat assessment (if necessary) is completed within the respective visit window and that the assessment is not done concurrently with other study procedures.
- 12. A single 12-lead ECG will be performed in the supine position after 10 minutes of rest.
- 13. Participants must fast for a minimum of 8 hours prior to samples being collected.
- 14. Samples should be collected prior to study drug administration.
- 15. Serum archive sample is not collected in China.
- 16. Only hsCRP will be assessed at Screening (Visit 1).
- 17. Urine dipstick analysis will be performed locally from a sample of mid-stream urine. In case of abnormal results, microscopy and other assessments will be performed at the local laboratory and the abnormality recorded as an AE.
- 18. A PK sample will be collected prior to study drug administration for trough measurement of obicetrapib in plasma. At Visits 2, 5, and 7, participants should take study drug after a trough PK sample has been drawn.
- 19. CV events include CV death, non-fatal myocardial infarction, non-fatal stroke, non-elective coronary revascularization, hospitalization for unstable angina and/or chest pain, hospitalization for heart failure, and transient ischemic attack.

ABPM = ambulatory blood pressure monitoring; AE = adverse event; ApoA1 = apolipoprotein A1; BMI = body mass index; CV = cardiovascular; ECG = electrocardiogram; EOS = End of Study; EOT = End of Treatment; ET = Early Termination; FSH = follicle-stimulating hormone; HOMA-IR = homeostatic model assessment of insulin resistance;

hsCRP = high sensitivity C-reactive protein; ICF = informed consent form; Lp(a) = lipoprotein (a); PK = pharmacokinetic(s); TSH = thyroid-stimulating hormone; UACR = urine albumin-creatinine ratio; UPCR = urine protein-creatinine ratio; V = Visit.

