- To evaluate the effect of obicetrapib on hospitalization for unstable angina and/or chest pain, hospitalization for heart failure (HF), transient ischemic attack (TIA), abdominal aortic aneurysm (AAA) and carotid revascularization.

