- The time from Randomization until the first confirmed occurrence of a composite of CV death, non-fatal MI, or non-fatal stroke, or coronary revascularization;
- The time from Randomization until the first confirmed occurrence of a composite of CV death, non-fatal MI, or non-fatal stroke; and
- The time from Randomization until the first confirmed occurrence of hospitalization for unstable angina and/or chest pain, hospitalization for HF, and TIA;
- The time from Randomization until the first confirmed occurrence of MALE event. The MALE event will include acute limb ischemia, major amputation, urgent revascularization.
- The time from Randomization until the first confirmed occurrence of a composite of CHD death, non-fatal MI, or non-fatal stroke, or non-elective coronary revascularization;

- The time from Randomization until the first confirmed occurrence of a composite of CHD death, non-fatal MI, or non-fatal stroke, or coronary revascularization;
- The time from Randomization until the first confirmed occurrence of a composite of CHD death, non-fatal MI, or non-fatal stroke;
- The time from Randomization until the first confirmed occurrence of a composite of CV death, non-fatal MI, non-fatal stroke, hospitalization of unstable angina, or non-elective coronary revascularization;
- The time from Randomization until the first confirmed occurrence of a composite of CV death, non-fatal MI, non-fatal stroke, hospitalization of unstable angina, or coronary revascularization;
- The time from Randomization until the first confirmed occurrence of a composite of CHD death, non-fatal MI, non-fatal stroke, hospitalization of unstable angina, or non-elective coronary revascularization;
- The time from Randomization until the first confirmed occurrence of a composite of CHD death, non-fatal MI, non-fatal stroke, hospitalization of unstable angina, or coronary revascularization;
- The time from Randomization until the first confirmed occurrence of a composite of CV death, non-fatal MI, non-fatal stroke, hospitalization of unstable angina, MALE, or non-elective coronary revascularization;
- The time from Randomization until the first confirmed occurrence of a composite of CV death, non-fatal MI, non-fatal stroke, hospitalization of unstable angina, MALE, or coronary revascularization;

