the following analysis will be performed. The participants who withdraw from the study before the occurrence of event or event did not occur will be censored. For these participants the time-to-event will be defined as time between Randomization and ET/EOS. Other atherosclerotic events such as AAA and carotid revascularization will be identified using the preferred terms (see [Appendix C](#)). The Clinical Events Committee (CEC) adjudicated date of event will be used to identify the first confirmed occurrence of event where appropriate, otherwise the date of event as recorded in eCRF will be used. In case when CEC cannot provide adjudicated date of death, the latest date of the last dose of study drug or date of last visit will be imputed as date of death for analysis.

The Log-rank Test

The log-rank test, stratified by CV risk (HeFH or non-HeFH), and Baseline statin therapy (HIS or non-HIS) will be used to compare differences in the time-to-event between obicetrapib and placebo.

The sample SAS code can be found below:

Note:

TREATMENT = 0 (Placebo), 1 (Obicetrapib)
CVRISK = 1 (HeFH), 2 (non-HeFH)
STATIN = 1 (HIS), 2 (non-HIS)
TIME = Time from Randomization until the first occurrence of event
CENSOR = 0 (Event occurred), 1 (Event did not occurred)

```
proc lifetest data= time_to_event method=KM  
    strata CVRISK STATIN/test=logrank group=TREATMENT;  
    time TIME*CENSOR;
```

Run;

Cox Proportional Hazard Model

A Stratified Cox proportional hazard model will be used to estimate hazard ratio between treatment groups along with the 95% confidence intervals. The model will include treatment group, CV risk (HeFH or non-HeFH), and Baseline statin therapy (HIS or non-HIS).

The Cox proportional hazard model will be implemented using SAS® Proc PHREG. The sample SAS code can be found below:

Note:

TREATMENT = 0 (Placebo), 1 (Obicetrapib)
CVRISK = 1 (HeFH), 2 (non-HeFH)
STATIN = 1 (HIS), 2 (non-HIS)
TIME = Time from Randomization until the first occurrence of event
CENSOR = 0 (Event occurred), 1 (Event did not occurred)

```
proc phreg data= time_to_event ;  
    model TIME*CENSOR=TREATMENT;  
    strata CVRISK STATIN;
```

Run;

The proportional hazard assumption will be evaluated via examination of complementary log-log (event time) versus log (time) plots. If the proportional hazard assumption raises concerns, the non-parametric Peto-Peto-Prentice test will be applied. Nominal p-values will be provided when applicable.

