APPENDIX C: PREFERRED TERMS FOR AAA AND CAROTID REVASCULARIZATION

Preferred Term for AAA	Preferred Term for carotid revascularization
Acute aortic syndrome	Carotid angioplasty
Aortic aneurysm	Carotid artery bypass
Aortic aneurysm repair	Carotid artery stent insertion
Aortic aneurysm rupture	Carotid artery stent removal
Aortic aneurysm syphilitic	Carotid endarterectomy
Aortic dilatation	Carotid revascularisation
Aortic dissection	
Aortic dissection rupture	
Aortic intramural haematoma	
False lumen dilatation of aortic dissection	
Penetrating aortic ulcer	

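### Carotid revascularization is searched for by procedure terms that sites are told not to record as AEs, and the AAA term list is not limited to abdominal or atherosclerotic disease

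*SAP*

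**What the plan says.** SAP 2.1.3 sets an exploratory objective that covers, in a single bullet, hospitalization for unstable angina or chest pain, hospitalization for heart failure, "transient ischemic attack (TIA), abdominal aortic aneurysm (AAA) and carotid revascularization". SAP 2.3.3 has no endpoint for AAA or carotid revascularization alone. Together with TIA they form the other atherosclerotic events component of its broadest composites.

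On how these events are found, SAP 3.4.3 says: "Other atherosclerotic events such as AAA and carotid revascularization will be identified using the preferred terms", and refers to Appendix C. It does not name the dataset to be searched. The event date is the one adjudicated by the Clinical Events Committee (CEC) where appropriate, and otherwise the eCRF date. Appendix C lists 11 terms for AAA and 6 for carotid revascularization.

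Protocol 8.2 says that the condition leading to a medical or surgical procedure "should be recorded as an AE, not the procedure itself". The same section keeps a condition already present at Screening in medical history unless it changes. Protocol 10.1.4 gives the scope of MedDRA coding: "Medical Dictionary for Regulatory Activities (latest) for medical history and AEs". Footnote 19 of the schedule (Protocol Appendix A, repeated under SAP Table 1) begins "CV events include CV death, non-fatal myocardial infarction, non-fatal stroke, non-elective coronary revascularization" and ends with the unstable angina, heart failure and TIA events. Neither AAA nor carotid revascularization is in it.

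**The concern.** The search terms and the recording rule do not meet. A site that follows the protocol writes down carotid stenosis, and a programmer who follows the SAP looks for endarterectomy or stenting. Events are then counted mainly where a site departs from the AE rule, so capture depends on site habit.

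The aortic list has the reverse fault. It accepts aortic diagnoses at any location, including ones that are not aneurysms, and labels them AAA.

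The composites that contain this component will be reported with hazard ratios or rate ratios and confidence intervals. If nothing changes, part of what they count will not match their label. A correction made after unblinding would be open to challenge.

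**Working it through.** The documents give no expected count, rate or power for these events, so there is no plan figure to reproduce. The check sets the term lists against the recording rules.

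**1. Carotid terms (SAP Appendix C).** The six are angioplasty, bypass, stent insertion, stent removal, endarterectomy and revascularisation. Procedures: 6 of 6. Stent removal is not itself a revascularization.

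**2. One participant followed through.** Carotid stenosis above 70% is a qualifying condition (Protocol 4.1, criterion 3). Suppose such a participant has an endarterectomy on Day 200.
- If the stenosis has worsened, Protocol 8.2 gives an AE of carotid stenosis. No Appendix C term matches.
- If it is unchanged, it stays in medical history. Protocol 8.3 does not record hospitalization for elective treatment of an unworsened pre-existing condition as an SAE. There may be no AE record at all.

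Medical history is also coded, but a match there on a past carotid procedure would be a pre-study event, not an endpoint.

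**3. Capture of carotid procedures through AE data.** Let n be the number of procedures and s the share that sites record as AEs against the rule. Captured = n × s. The documents give no value for s, so the assumed range is 0 to 1. For n = 10:
- s = 0: 10 × 0 = 0
- s = 0.25: 10 × 0.25 = 2.5
- s = 0.5: 10 × 0.5 = 5
- s = 1: 10 × 1 = 10

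**4. AAA terms (SAP Appendix C), 11 in all.**
- Restricted to the abdominal aorta: 0.
- Containing the word aneurysm: 4 (aneurysm, repair, rupture, syphilitic). Not containing it: 11 − 4 = 7 (acute aortic syndrome, dilatation, dissection, dissection rupture, intramural haematoma, false lumen dilatation, penetrating ulcer).
- Non-atherosclerotic by name: 1, "Aortic aneurysm syphilitic".
- Procedures: 1 (repair). The other 11 − 1 = 10 are conditions that the AE rule allows.

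**5. Endpoints affected (SAP 2.3.3).** The component appears with CV death or CHD death, crossed with non-elective or all coronary revascularization: 2 × 2 = 4 time-to-event composites. The same four recur as total-event counts: 4 + 4 = 8.

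**6. Illustration of the over-inclusive list, on assumed values.** Let p be the share of the aortic event rate that is true AAA. Assume a hazard ratio of 0.70 for AAA and 1.0 for the other aortic terms. The aortic component then shows p × 0.70 + (1 − p) × 1.0, which is 0.70, 0.775, 0.85 and 0.925 for p = 1, 0.75, 0.5 and 0.25. This describes the aortic component only. The shift in a full composite depends on how few or many of its events are aortic, which the documents do not say.

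**The case against.** The strongest defence is that the search is not the only possible route. Protocol 8.1 sends all potential or suspected CV events to the CEC and a clinical endpoint eCRF, and SAP 3.4.3 does not restrict the search to AE data. The CEC charter and the eCRF are not available to check. Sites may also record procedures despite the rule. A reader might therefore infer from the term lists that the objective cannot be answered, or that carotid capture will be zero, and the documents do not support that. Zero needs full compliance with the AE rule and no capture by the endpoint eCRF. On the aortic side only 1 of 11 terms meets the procedure rule, and the general aneurysm terms can still find an AAA. The fault there is poor specificity, not absent data.

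What remains is that neither event is on the list of CV events assessed at visits, and that the SAP itself chose a preferred-term search.

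A reader might also extend the point to the composites that add limb events or all coronary revascularization. That does not follow. SAP 3.4.3 applies the term search only to AAA and carotid revascularization. The limb endpoint is defined separately ("The MALE event will include acute limb ischemia, major amputation, urgent revascularization"), and Protocol 7.2.4 defines coronary revascularization in general before it defines the non-elective subset.

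Finally, only the syphilitic term is non-atherosclerotic on its face. Striking out dissection, haematoma, ulcer or dilatation would rest on clinical judgement that the documents do not supply.

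**Conclusion.** The point holds in this form: carotid revascularization will be under-ascertained, possibly to zero, and AAA will be ascertained over-inclusively, so this part of the objective in SAP 2.1.3 is not reliably answerable as specified. All 6 carotid terms conflict with the AE rule. None of the 11 aortic terms is limited to the abdomen, 7 do not mention aneurysm, and 1 is non-atherosclerotic by name.

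The conclusion assumes that sites largely follow Protocol 8.2 and that the search runs on coded AE data, the natural reading given the coding scope in Protocol 10.1.4. Because sites are blinded, the documents give no reason to expect carotid capture to differ between arms. The expected harm is lost events and a mislabelled component, not a demonstrated bias in favour of either group.

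The reach is limited to 8 exploratory composites without multiplicity adjustment and one joint exploratory objective. Primary and secondary endpoints, and the narrower cardiovascular composites, are unaffected.

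**What to change.** 1. In SAP 3.4.3, name the dataset that is searched. Before unblinding, run one blinded site query to confirm whether a carotid procedure took place and on what date. Trigger it by any AE of carotid stenosis, by carotid stenosis in medical history, and by any Appendix C term. Count the confirmed procedures instead of relying on the term match alone.
2. In Appendix C, remove the carotid stent removal and syphilitic aneurysm terms. For the remaining aortic terms, either confirm abdominal location in the same query and count only those events as AAA, or keep the list and relabel the component as aortic events in the 8 composites.

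The cost is one blinded query round, some site effort and SAP wording. Adding both events to footnote 19 and collecting them prospectively would be cleaner, but under Protocol 12.1 that is an amendment needing full review and approval, with collection across about 180 sites. For exploratory endpoints the query is the proportionate route.

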3.4.4 Subgroup Analysis

The primary efficacy endpoints also will be analyzed by the following subgroups:

- Age categories (<65 years, 65 to 74 years, and 75+ years)
- Sex (male, female)
- Race (white, Asian, Black or African American, Other)
- Ethnicity (Hispanic/Latino, Not Hispanic/Latino)
- BMI (<25 kg/m², 25 -30 kg/m², ≥30 kg/m²)
- Region (Asia, Eastern Europe, Western Europe and North America)
- Country (USA vs Other, Japan vs Other, China vs Other)
- Diabetes (yes, no)
- HDL-C (<40mg/dL, 40 - <60 mg/dL, ≥60mg/dL)
- ApoB (<60mg/dL, 60 - <90 mg/dL, ≥90mg/dL)
- ApoA1 (<110 mg/dL, ≥110 and <125 mg/dL, ≥125mg/dL)

- Lipoprotein(a) (<75nmol/L, ≥ 75 and <125 nmol/L, ≥ 125 nmol/L)
- Non-HDL-C (<100 mg/dL, ≥ 100 and <130 mg/dL, ≥ 130 mg/dL)
- LDL-C (<70mg/dL, ≥ 70 and <100 mg/dL, ≥ 100 mg/dL)
- TG (<150 mg/dL, ≥ 150 mg/dL)
- HbA1c (<5.7%, ≥ 5.7 to ≤ 6.4 %, >6.4 %)
- Urinary albumin:creatinine ratio (normal, micro-albuminuria, macro-albuminuria)
- eGFR (<30ml/min/1.73 m², ≥ 30 to <45ml/min/1.73 m², ≥ 45 to <60ml/min/1.73 m², ≥ 60 to <90ml/min/1.73 m², ≥ 90 ml/min/1.73 m²)
- Statin treatment (high dose, low or moderate dose, none)
- Ezetimibe use (yes, no)
- GLP1 use (yes, no)
- SGLT2 use (yes, no)
- Hs-CRP (<2mg/dL, ≥ 2 mg/dL)
- HeFH (Genotyping confirmed or DLCN>8 points or Simon Broome definite; Simon Broome possible FH diagnosis).

The ANCOVA model with fixed effects for the treatment group, subgroup variable, treatment-by-subgroup variable, along with CV risk (HeFH or non-HeFH) and Baseline statin therapy (HIS or non-HIS) and covariates of Baseline LDL-C will be used. The CV risk and Baseline statin therapy covariates may be excluded from the model in cases where inclusion causes the model not to converge. The least squares (LS) mean, standard errors, and 2-sided 95% confidence intervals for each treatment group and for the mean difference compared to placebo, within each level of the subgroup, will be estimated. No imputation of missing data will be performed; therefore, the subgroup analysis will perform using only observed data. For the primary efficacy endpoint, the LDL-C values measured by preparative ultracentrifugation will be used. However, if the analysis for the primary efficacy endpoint specified above will show a difference between the 3 LDL-C approaches, then Friedewald and Martin-Hopkins equations may be considered for subgroup analysis.

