    - Current daily cigarette smoking;
    - Age of >60 years;
    - High sensitivity C-reactive protein (hsCRP) ≥2.0 mg/L (≥19.0 nmol/L) at Screening (Visit 1) or within 6 months prior to Screening (Visit 1);
    - Fasting TG >150 mg/dL (>1.7 mmol/L);
    - Fasting Lp(a) > 30 mg/dL (>70 nmol/L); and/or
    - Fasting HDL-C <40 mg/dL (<1.0 mmol/L).

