3.1.6 Hypothesis Testing

The hypothesis testing of the percentage change in LDL-C from Baseline to Day 84 is statistically defined as:

$$H_0: \mu_1 - \mu_0 = 0, H_1: \mu_1 - \mu_0 \neq 0,$$

where μ_0 - the percentage change in LDL-C in the placebo group,

μ_1 - the percentage change in LDL-C in the obicetrapib group.

A fixed sequential testing procedure will be implemented in order to control the Type I error rate. In a hierarchical step-down manner, the primary endpoint will be tested first, followed by the secondary efficacy endpoints in a pre-specified order (see [Section 3.4.2](#)). No adjustment for multiple comparison will be made for the exploratory efficacy endpoints.

The hypothesis testing of the change in average systolic blood pressure (SBP) measured by 24-hour ABPM from Baseline to Day 270 is defined as follows:

$$H_0: \mu_T - \mu_P \geq 3 \text{ mmHg}, H_1: \mu_T - \mu_P < 3 \text{ mmHg}$$

where μ_P - the change in average SBP in the placebo group,

μ_T - the change in average SBP in the obicetrapib group.

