- Urinary albumin:creatinine ratio (normal, micro-albuminuria, macro-albuminuria)
- eGFR (<30ml/min/1.73 m², ≥30 to <45ml/min/1.73 m², ≥45 to <60ml/min/1.73 m², ≥60 to <90ml/min/1.73 m², ≥90ml/min/1.73 m²)
- Statin treatment (high dose, low or moderate dose, none). High dose statin will be defined as atorvastatin 40 or 80 mg, rosuvastatin 20 or 40 mg. Participants will be defined as having high dose statin based on the data collected in the eCRF and if any following were used at baseline: average daily dose of atorvastatin ≥40 mg or average daily dose of rosuvastatin of ≥20 mg. For Japan only, high dose statin includes atorvastatin 10 or 20 mg for non-familial hypercholesterolemia, atorvastatin 20 or 40 mg for heterozygous

familial hypercholesterolemia, rosuvastatin 10 or 20 mg. Participants will be defined as having high dose statin treatment, for Japan only, if any following were used at baseline: average daily dose of atorvastatin ≥ 10 mg or average daily dose of rosuvastatin of ≥ 10 mg. Participants having other doses of statin or other statin treatment will be defined as low or moderate.

- Ezetimibe use (yes, no)
- Glucose-like peptide-1 (GLP1) use (yes, no)
- Sodium-glucose co-transporter-2 (SGLT2) use (yes, no)
- A high-sensitivity C-reactive protein [hs-CRP] (<2 mg/dL, ≥ 2 mg/dL)
- HeFH (yes, no)
- HIS, non-HIS
- HeFH (Genotyping confirmed or DLCN>8 points or Simon Broome definite); Simon Broome possible Familial Hypercholesterolemia (FH) diagnosis.

If they differ from the ITT Population, summaries will also be provided for the FAS, the mITT Population, mITT On-Treatment Population, the PP Population, and the Safety Population. Demographic characteristics data will be provided in participants listings.

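### SAP 3.3.4 and 3.4.4 split hs-CRP at 2 mg/dL, ten times the protocol's 2.0 mg/L threshold; the unit needs correcting in both places

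*SAP*

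**What the plan says.** The hs-CRP threshold appears in three roles.

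- **Eligibility.** Protocol 4.1, inclusion criterion 5 (repeated in the Synopsis), lists as one of eight risk enhancers for the lower LDL-C/non-HDL-C band: "High sensitivity C-reactive protein (hsCRP) ≥2.0 mg/L". The SI value beside it is 19.0 nmol/L.
- **Baseline table.** SAP 3.3.4 categorises "A high-sensitivity C-reactive protein [hs-CRP] (<2 mg/dL", with the upper category starting at the same value.
- **Subgroup analysis.** SAP 3.4.4 says "The primary efficacy endpoints also will be analyzed by the following subgroups" and lists hs-CRP with the same 2 mg/dL cut.

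The subgroup model is described as "The ANCOVA model with fixed effects for the treatment group, subgroup variable, treatment-by-subgroup variable", with the stratification factors and baseline LDL-C added. Its stated output is LS means, standard errors and 95% confidence intervals for each group and "for the mean difference compared to placebo, within each level of the subgroup, will be estimated". Ultracentrifugation LDL-C is the subgroup version. If the three LDL-C methods give different results on the primary endpoint, "then Friedewald and Martin-Hopkins equations may be considered for subgroup analysis".

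**The concern.** The numeral 2 is the same in protocol and SAP, but the unit is not. Because mg/dL appears in two separate SAP sections, it cannot be dismissed as an isolated slip, and a programmer working from the SAP has no instruction to read it as mg/L.

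Two outputs are affected if the rule is followed literally. The baseline table would place everyone between 2 and 20 mg/L in the lower category, and so understate the number at or above the level the protocol treats as raised. The subgroup analysis would contrast participants with markedly elevated hs-CRP against everyone else, rather than compare the two sides of the protocol's threshold. The upper-level estimate would probably rest on few participants.

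**Working it through.** **Inputs from the documents.** Randomised 2400 in a 2:1 ratio; 5% dropout; 2280 evaluable; SD 15%; planned difference 30%; one-sided 0.025 (SAP 2.2.1 and 2.2.2). SAP 3.4.4 gives no precision or power of its own, so the only plan figure to reproduce is the overall one.

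**1. The plan's figure.** 2400 × 0.95 = 2280, that is 760 placebo and 1520 obicetrapib. SE = 15 × √(1/760 + 1/1520) = 0.67, and 30/0.67 is about 45, so power is effectively 1.000. This agrees with the stated figure of more than 90%.

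**2. Unit.** 1 mg/dL = 10 mg/L, so 2 mg/dL = 20 mg/L. The protocol's pair gives 19.0/2.0 = 9.5 nmol per mg, so the SAP cut corresponds to 20 × 9.5 = 190 nmol/L, against 19.0 nmol/L in the protocol. The ratio is exactly 10, and the SI value confirms that mg/L is what the protocol means.

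**3. Share in the upper level (assumed distribution).** No hs-CRP distribution is given in either document. Take a log-normal with median m and log-SD s, so that the share at or above c is 1 − Φ[(ln c − ln m)/s].

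| m (mg/L) | s | ≥20 mg/L | of 2400 | ≥2 mg/L |
|---|---|---|---|---|
| 1 | 0.9 | 0.04% | 1 | 22.1% |
| 1 | 1.3 | 1.06% | 25 | 29.7% |
| 2 | 0.9 | 0.53% | 13 | 50.0% |
| 2 | 1.1 | 1.82% | 44 | 50.0% |
| 2 | 1.3 | 3.83% | 92 | 50.0% |
| 3 | 0.9 | 1.75% | 42 | 67.4% |
| 3 | 1.3 | 7.22% | 173 | 62.2% |

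The upper level as written holds 0.04% to 7.2% of participants; at the protocol's cut it would hold about 22% to 67%. The difference between the two columns is the share the baseline table would place in the lower category although they meet the protocol's threshold. For example, 50.0% − 1.8% = 48.2% at m = 2 and s = 1.1. The extremes are about 22% (m = 1, s = 0.9) and 66% (m = 3, s = 0.9).

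**4. Precision in the upper level.** With N participants split 2:1 and SD 15, the 95% half-width is 1.96 × 15 × √(1/(N/3) + 1/(2N/3)) = 29.4 × √(4.5/N).

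- 0.5% of 2280 (N = 11.4): 18.5 points
- 2% of 2280 (N = 45.6): 9.2 points
- 5% of 2280 (N = 114): 5.8 points
- 50% of 2280 (N = 1140): 1.8 points

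**The case against.** The strongest reply is that mg/dL is only a typing error. If the programs apply 2 to data held in mg/L, the split is roughly balanced. The programming specifications are a separate document (SAP section 7), so this cannot be excluded. It does not rescue the text: either the output follows the SAP and uses the wrong cut, or it departs from the SAP and may carry the wrong unit label.

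It is also fair to say that the damage is bounded. Eligibility follows the protocol, not the SAP. hs-CRP is collected at Screening, Visit 2 and Visit 7, so a 2 mg/L split can always be recovered from the data. Even a half-width of 9 points would exclude zero at the planned 30-point effect. A reader might infer that the upper level is nearly empty, or that the trial could not report the effect at raised hs-CRP. The first depends on a distribution the documents do not give, and the second is not so.

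A reader might also infer something larger: that the length of the subgroup list makes a spurious interaction likely. The list has 24 variables, and "Country (USA vs Other, Japan vs Other, China vs Other" is three contrasts, so there are 26 models. Testing each interaction at 0.05 with no true heterogeneity gives 1 − 0.95^26 = 74% for at least one nominal finding if the tests are independent. Simulation with equal correlation gives 62% at 0.3, 47% at 0.5 and 32% at 0.7. The documents do not support this as an error. SAP 3.4.4 names no interaction test, p-value or alpha and plans within-level intervals. Many factors overlap (LDL-C, non-HDL-C and ApoB; diabetes and HbA1c; race, region and country). Subgroups also lie outside the fixed testing sequence. The sentence "No adjustment for multiple comparison will be made for the exploratory efficacy endpoints" does not literally cover subgroups of the primary endpoint, but that is a missing label rather than a faulty analysis.

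Nor is the LDL-C formula option selection on subgroup results. Its trigger is disagreement between measurement methods in the overall analysis, and ultracentrifugation is already fixed as the subgroup version. What stands is that the size of disagreement is undefined.

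**Conclusion.** The hs-CRP cut is wrong as written in SAP 3.3.4 and 3.4.4: 20 mg/L where the protocol's threshold is 2.0 mg/L. The factor of ten is certain and rests on the documents alone. The consequences are probable rather than certain. Under the assumed log-normals the upper level is sparse, and the baseline table understates the number meeting the protocol's raised-hsCRP threshold. The precision loss (about 9 points against 1.8 in the 2% case) also assumes the planning SD of 15% and 2:1 allocation within the level.

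The primary estimate, its test and the fixed sequence are untouched. The matter deserves correction because a literal reading misclassifies participants in two planned outputs, not because any confirmatory conclusion is at risk.

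**What to change.** In SAP 3.3.4 and 3.4.4, change the hs-CRP categories to <2 mg/L and ≥2 mg/L, and check that the programming specifications and table shells carry the same unit. The cost is two wording changes, with no new data, model or analysis.

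Two clarifications are optional. One is a sentence in 3.4.4 stating that subgroup analyses are exploratory, and whether interaction p-values will be shown as nominal. The other is a definition, fixed before unblinding, of how large a difference between the LDL-C methods would prompt the alternative-formula subgroup tables. Defining that trigger is preferable to deleting the option, because deletion would give up a reasonable sensitivity check for the case where the methods disagree.
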